8.3 Study Intervention

8.3.1 Dosing During Taper

Taper guidelines are provided in **Table 8.1** (Phase 1) and **Table 8.2** (Phase 2) for participants on stabilization doses of 8, 16, 24, and 32 mg BUP (with appropriate corresponding amounts of naloxone, i.e., 2 mg NX for each 8 mg BUP). The study medical clinician may deviate from the guidelines and individualize the taper to the extent indicated by clinical considerations (missed doses, emergent withdrawal signs, etc.) but the taper must be completed within the specified timeframe, and the dosing schedule recorded on the appropriate form.

Table 8.1 Phase 1 Dose Taper Schedule Using BUP/NX Tablets (Over 14 Days)

Taper Day	Stabilization Dose			
	32 mg	24 mg	16 mg	8 mg
1-2	32	24	16	8
3-4	24	16	12	6
5-6	16	12	10	6
7-8	12	10	8	6
9-10	8	8	8	4
11-12	6	6	6	4
13	4	4	4	2
14	2	2	2	2

Table 8.2 Phase 2 Dose Taper Schedule Using BUP/NX Tablets (Over 28 Days)

Taper Day	Stabilization Dose			
	32 mg	24 mg	16 mg	8 mg
1-3	32	24	16	8
4-6	24	16	12	6
7-9	16	12	10	6
10-12	12	10	8	6
13-15	10	8	8	4
16-18	8	6	6	4
19-21	6	4	4	4
22-24	4	4	4	2
25-27	2	2	2	2
28	2	2	2	2

8.3.2 Dispensing of Study Medication

BUP/NX will be dispensed for the first day of dosing by a medical clinician at each study site in accordance with state and federal regulations. Participants will be seen once again in Week 1 and then once weekly thereafter for dispensing of BUP/NX and clinical assessments. Take-home doses of BUP/NX will be provided to participants to self-administer at home on days between clinic visits. An additional visit may be occasionally required to adjust a participant's dose, or dispense additional medication to accommodate an increased dosage.

Participants receiving BUP/NX will be instructed to hold the tablet(s) under their tongue until the tablet(s) have completely dissolved. This may take several minutes. The tablet(s) should not be swallowed. A medical clinician will monitor dissolution of tablets at each study site. It is recommended that the participants be observed for at least 1 hour on the first day of treatment following the administration of BUP/NX.

8.3.3 Drug Packaging/Handling/Storage/Accountability

BUP/NX combination (Suboxone®) is available as a sublingual tablet in two doses: 2 mg BUP with 0.5 mg NX and 8 mg BUP with 2 mg NX. Study medication will be distributed to investigational sites in bottles of 30 sublingual tablets, and labeled with "For Experimental Use Only, Not to be Sold." The site investigator or pharmacist will be responsible for maintaining the study drug inventory and notifying NIDA (or designee) for replacement materials. Accurate recording of all BUP/NX received, dispensed, administered, returned, or destroyed will be made.

This is an open-label study. Each site will prepare individual prescriptions for each participant visit. These prescriptions will be provided in participant-numbered, child resistant packaging and clearly labeled with local regulatory requirements.

All study drug will be stored in the controlled access of the facility in compliance with local and federal regulations. Store at 25°C (77°F), with excursions permitted to 15-30°C. Unused drug supply will be returned to a NIDA-designated location at the completion of the study.

8.4 Training Procedures

Training procedures are described in the Operations Manual. EMM interventionists will be substance abuse or mental health professionals (e.g., counselors, social workers, psychologists, nurses) employed by the CTP. SMM interventionists will be licensed medical clinicians.

9.1 General Considerations

A number of participants entering this trial will have pain, and many will be receiving other medications (e.g., non-steroidal anti-inflammatory drugs, gabapentin, antidepressants) and/or non-pharmacologic treatments (e.g., acupuncture, physical therapy, hypnosis) to assist them with their pain. Indeed, some participants, although medically stable, will be enrolled in pain management programs and will be referred to this study because their opioid use is out of control and the participant and his/her physician agree that discontinuing opioids would be advisable. This trial will not restrict the use of concomitant medications used by a participant's outside physician for pain management with the exception of opioids. Concomitant other treatments will be assessed at each scheduled visit and recorded.

9.2 Medications Allowed During the Trial

Prior to study initiation (induction) participants should not have taken or been administered any opioid medications or heroin for approximately 12 hours.

9.2.1 *Ancillary Detoxification Comfort Medications*

All participants will have the option to receive ancillary detoxification comfort medications during stabilization, during the taper, and beyond the taper. Study physicians should limit the duration of the prescription to the time in which a subject is enrolled in that phase of the study. Use of any medications will be recorded on a CRF. Prescribing of ancillary medications will be at the physician's discretion in accordance with clinical need to assist with the management of withdrawal symptoms but should be limited only to those medications listed below. Each participant will be instructed on the use of each medication prescribed and told they can self-administer the medication in accordance with the instructions. The use of ancillary medications will be closely monitored for the duration of the study. The following list provides the typical dose, schedule and indication for ancillary medication use:

- *For anxiety and restlessness:* hydroxyzine hydrochloride 50 mg, po q6 hrs prn; not to exceed 200 mg per 24 hrs
- *For bone pain and arthralgias:* non-steroidal anti-inflammatory agent (NSAID) such as ibuprofen (Advil, Motrin and others-use within current guidelines) 800 mg po q8 hrs with food, not to exceed 2400 mg per 24 hrs; if an NSAID is not appropriate, acetaminophen – not to exceed 3 gm/day

- *For abdominal cramps:* dicyclomine (Bentyl) 20 mg QID, increase up to 40 mg QID (usual daily maximum 160 mg)
- *For nausea:* trimethobenzamide (Tigan) 300 mg po q8 hrs prn, not to exceed 900 mg per 24 hrs. OR prochlorperazine (Compazine) 5 - 10 mg TID/QID (usually daily maximum 40 mg) OR promethazine (Phenergan) 12.5-25 mg Q4-6 hours as needed
- *For diarrhea:* loperamide (Immodium) 2 mg, 2 caps followed by 1 cap after each unformed stool; not to exceed 8 mg per 24 hrs OR Donnatal 1-2 tablets po q6-8 hrs prn; not to exceed 8 tablets/day
- *For insomnia:* trazodone hydrochloride 50 mg, 1-4 tabs, po qhs prn OR doxepin hydrochloride 50 mg, 1-3 tabs, po qhs prn OR diphenhydramine 25-50 mg, may repeat once up to 100mg, OR zolpidem tartrate (Ambien) 10 mg, 1-2 tabs, po qhs prn OR ramelteon (Rozerem) One 8 mg tablet 30 minutes prior to bedtime

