1.2.1.4 Phase 1 Study Design

All participants will be administered BUP/NX in a 1-day induction regimen, which begins the 4-week BUP/NX treatment phase. Participants will also be randomly assigned to either SMM or EMM (both described below). Randomization will be stratified within site with respect to chronic pain and lifetime heroin use to decrease the likelihood of meaningful imbalances between the treatment groups with respect to the potentially important factors ‘chronic pain’ and ‘lifetime heroin use.’ Participants will be seen twice during the first week of treatment.

The following induction algorithm is proposed:

1. Participants should refrain from opioid use for approximately 12 hours prior to induction.
2. Pre-dose baseline score on COWS should be greater than 8 (no signs of intoxication).
3. An initial 4 mg sublingual dose should be given and the participant observed for 1 hour. If symptoms improve (COWS score reduced by at least 2 points), the participant can be sent home with two 4 mg doses and instructed to take the additional doses if needed. If symptoms do not improve or worsen, an additional 4 mg is given and the participant observed for another hour and sent home with the remaining 4 mg dose.
4. The study medical clinician or a designated staff member should contact the participant by phone later the first day.

This induction scheme is relatively conservative and limits the first day dose to 12 mg. Alternative induction schedules, in which participants receive up to 16 mg in the first day, can be used if the study medical clinician believes it is necessary. These alternative induction schedules are described in the Operations Manual.

Including induction, all participants will receive BUP/NX for four weeks. At each visit during this phase, the study medical clinician may adjust the BUP dose in increments of up to 8mg. The maximum allowable dose is 32mg per day. Dose changes are to be determined after the study staff obtains vital signs, evaluation of illicit drug use (urine and self-report), craving, signs and symptoms of opiate withdrawal or over-medication, adverse events and current BUP/NX and other medication taken since the last visit. During Weeks 3 and 4 participants will taper off BUP/NX to zero dosage. Taper will begin around Study Day 15 and must end by Study Day 28.

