9. Participants must be non-psychotic and psychiatrically stable in the opinion of the study investigator.
10. Participants will be asked to provide locator information including their residential street address and a working telephone number; or, if they are homeless, they must provide the address and telephone number of a non-drug abusing relative or friend who can reach the participant in emergencies.
11. Prior to induction:
 - Participant should be in opioid withdrawal (COWS scale >8)
 - Participant's dose of methadone (if receiving it for pain; those receiving methadone treatment for opioid dependence are excluded, see below) should be less than or equal to 40 mg

Participants will be excluded if they:

1. Have a medical condition that would make participation medically hazardous, in the opinion of the study investigator, after consultation with the study physician (if not the same), based on a review of medical records and baseline evaluations.
2. Have known allergy or sensitivity to buprenorphine or naloxone.
3. Are psychotic or have any other acute severe psychiatric condition.
4. Are a suicide risk within the past 30 days.
5. Are dependent on alcohol, sedative-hypnotics or stimulants, and requiring immediate medical attention.
6. Have used heroin more than four days in the past 30 days.
7. Have participated in another investigational drug study within the last 30 days.

8. Have participated in methadone or buprenorphine maintenance treatment for opioid dependence within 30 days of study enrollment.
9. Have a current or pending legal status that would make them unlikely to remain in the local area for the duration of the study.
10. Lifetime opioid dependence that would be accounted for by heroin use alone.
11. Have ever used heroin by injection.
12. Have experienced a traumatic or major pain event within the past six months.
13. Are pregnant or lactating or a female unwilling to follow study required measures for pregnancy prevention.
14. Are unable to remain in the local area for the duration of Phases 1 and 2 of the study.
15. Have presence of pain of sufficient severity as to require ongoing pain management with opioids.
16. Have LFTs >5x upper limit of normal range.
17. Have surgery scheduled within the next six months that would preclude participation during the active treatment phase of the study.
18. Are currently receiving formal substance abuse treatment.

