1.4.1.1 Induction Schedule - Day 1 of Treatment

Day One: All participants should refrain from opioid use for approximately 12 hours prior to induction. Pre-dose baseline scores on COWS should be greater than eight (8) (no signs of intoxication).

An initial four (4) mg dose of BUP/NX (two sublingual tablets with 2mg BUP/0.5mg NX) will be administered, and the participant observed for 1 hour. If symptoms improve (improvement of two points on COWS), the participant can be sent home with two 4mg doses and instructed to take the additional doses if needed.

If symptoms do not improve, or worsen, an additional 4mg is administered and the participant observed for another hour and sent home with the remaining 4mg dose.

Study investigators will contact the participant by phone later during the first day.

This one-day induction limits the first day's dose to 12 mg. Alternative induction schedules allowing a first-day dose of 16mg will be described in the Operations Manual.

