4.1.1 Phase 1 Induction and Treatment

4.1.1.1 Induction

For the 1-day induction phase:

- All participants should refrain from opioid use for approximately 12 hours.
- Pre-dose baseline scores on COWS should be greater than eight (8) (no signs of intoxication but not in serious withdrawal).
- An initial 4 mg dose of BUP/NX (two sublingual tablets with 2 mg BUP/0.5 mg NX) will be administered, and the participant observed for 1 hour.
 - If symptoms improve (at least a 2-point reduction in COWS score), the participant can be sent home with two 4 mg doses and instructed to take the additional doses if needed.
 - If symptoms do not improve, or worsen, an additional 4 mg is administered; the participant is observed for another hour, and sent home with the remaining 4 mg dose.
- All participants will be sent home with additional doses of BUP/NX to last until the next study visit, which will also be scheduled during the first week of treatment.
- Study staff will contact the participant by phone later during the first day.
- This 1-day induction limits the first day dose to 12 mg. Alternative induction schedules allowing a first-day dose of 16mg will be described in the Operations Manual.

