5.1.1.1 Inclusion Criteria

1. Participants must have the ability to read, understand (including passing a comprehension quiz), and provide written informed consent.
2. Participants must be 18 years of age or older
3. Females of childbearing capacity must agree to use an acceptable method of birth control throughout the study. One of the following methods of birth control is acceptable for females:
 - a. hormonal contraceptives, including:
 - i. oral contraceptives
 - ii. intrauterine progesterone contraceptive system (IUD)
 - iii. levonorgestrel implant
 - iv. medroxyprogesterone acetate contraceptive injection
 - v. other hormonal method(s) approved by the study investigator

- b. barrier (diaphragm or cervical cap) with spermicide or condom
 - c. complete abstinence from sexual intercourse
 - d. male partner sterilization
4. Participants who are receiving opioids for pain must have clearance from their prescribing physician to enter the trial.
 5. Participants must have the ability to meet study requirements.
 6. Participants must meet DSM-IV criteria for current opioid dependence.
 7. Participants must be currently physically dependent on opioids (using prescription opioids at least 20 days/month) and in need of medical assistance for opioid withdrawal.
 8. Participants must be in good general health (in the opinion of the study investigator after review of medical records and baseline evaluations) or, for participants requiring ongoing medical/psychiatric treatment (whether currently in such treatment or not), under the care of a physician willing to continue participants' medical management and to cooperate with study site investigators.
 9. Participants must be non-psychotic and psychiatrically stable in the opinion of the study investigator.
 10. Participants will be asked to provide locator information including their residential street address and a working telephone number; or, if they are homeless, they must provide the address and telephone number of a non-drug abusing relative or friend who can reach the participant in emergencies.
 11. Prior to induction:
 - Participant should be in opioid withdrawal (COWS scale >8)
 - Participant's dose of methadone (if receiving it for pain; those receiving methadone treatment for opioid dependence are excluded, see below) should be less than or equal to 40 mg

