12.2.1.1 Known Potential Toxicities of Study Drug/Intervention

Potential toxicities of BUP include: deaths, which have been reported among people who abuse BUP in combination with benzodiazepines; withdrawal, if BUP/NX is taken within 24 hours of using methadone; increased risk of opiate dependence or death with continued use of heroin or other opiates; and possible impairment of mental or physical abilities for at least 6 hours after taking BUP/NX.

12.2.1.2 Known Potential Adverse Events Related to the Underlying Clinical Condition and/or Study Population

Side effects from BUP/NX may include headache, constipation, difficulty sleeping, weakness, sleepiness, nausea, vomiting, sweating, and dizziness. Elevated liver enzyme levels have been reported in participants with hepatitis that are treated with buprenorphine.

As with any new medication, the long-term side effects of BUP/NX are unknown at the present time.

Buprenorphine itself may cause physical dependence. It can also cause intoxication and mild respiratory depression, as evidenced by possible drowsiness and breathing that is slower and shallower.

If the participant attempts to dissolve and inject BUP/NX, he/she may experience opiate withdrawal symptoms, including nausea, diarrhea, hot and cold sweats, hot flashes, muscle cramps, flushing, painful joints, yawning, restlessness, watery eyes, runny nose, chills, gooseflesh, sneezing, abdominal cramps, irritability, backache, tension and jitteriness, depression, sleepiness, shaking or tremor, sensitivity to noise, clammy or damp skin, or other unpleasant effects. Use of other opiates while receiving the BUP/NX tablet could also result in opiate withdrawal symptoms.

The commercial formulation of BUP/NX has been classified Pregnancy Category C. Women of childbearing potential will be required to have a pregnancy test done before the first dose is given, and must agree to use an adequate method of contraception to avoid pregnancy while on BUP/NX.

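### The 12-hour opioid-free rule before induction permits BUP/NX 12 to 24 hours after methadone, inside the protocol's own 24-hour withdrawal warning

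*Protocol*

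**What the plan says.** The protocol gives the opioid-free interval before induction in four places, each time as about 12 hours and without distinguishing between opioids:

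- Section 1.2.1.4: "Participants should refrain from opioid use for approximately 12 hours prior to induction".
- Section 1.4.1.1: "All participants should refrain from opioid use for approximately 12 hours prior to induction".
- Section 4.1.1.1: "All participants should refrain from opioid use for approximately 12 hours".
- Section 9.2: "participants should not have taken or been administered any opioid medications or heroin for approximately 12 hours".

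Inclusion criterion 11 (1.3.1 and 5.1.1.1) adds two conditions. The first is a withdrawal score: "Participant should be in opioid withdrawal (COWS scale >8"). The second concerns methadone alone. The participant's "dose of methadone (if receiving it for pain") "should be less than or equal to 40 mg". Methadone maintenance for opioid dependence within 30 days of enrollment is excluded by exclusion criterion 8.

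Section 12.2.1.1, on known toxicities, includes "withdrawal, if BUP/NX is taken within 24 hours of using methadone".

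**The concern.** The authors treated methadone as a special case at induction, but they limited its dose and not its timing. The only methadone-specific time in the protocol is the 24 hours in the toxicity section, and it does not appear in the induction text that sites work from. A clinician who follows that text exactly can give BUP/NX at a time the protocol elsewhere associates with withdrawal.

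What is at stake is participant safety on day one. Section 1.4.3 also lists precipitation of withdrawal among the reported side effects. Under 12.2.1.3, withdrawal symptoms are not counted as adverse events in this study. COWS would record such an episode at a visit, but adverse event reporting would not normally flag it. That is a reason to prevent it through the induction rule.

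Methadone exposure is foreseeable. Criterion 11 expressly contemplates participants taking it for pain, and methadone is on the urine panel (10.2.1, 10.2.3.1). The 40 mg ceiling is worded for methadone received for pain, and criterion 4 asks for prescriber clearance from those receiving opioids for pain. Neither is worded for non-prescribed methadone.

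**Working it through.** No sample size, power or error rate is involved, so the check compares the stated intervals and looks for any place that reconciles them.

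**Inputs**

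- Interval required before induction: about 12 hours, any opioid (1.2.1.4, 1.4.1.1, 4.1.1.1, 9.2).
- Withdrawal score required: COWS above 8 (1.3.1, 5.1.1.1, repeated in 1.2.1.4, 1.4.1.1 and 4.1.1.1).
- Methadone condition: 40 mg or less if received for pain; no time since last dose (1.3.1, 5.1.1.1).
- Interval in the toxicity warning: 24 hours after methadone (12.2.1.1).

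**Step 1: width of the unreconciled window.** 24 h − about 12 h = about 12 h.

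**Step 2: is there a methadone-specific interval anywhere in the Phase 1 pre-induction text?** Seven places bear on it:

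| Section | Interval for all opioids | Methadone-specific condition | Methadone-specific interval |
|---|---|---|---|
| 1.2.1.4 | about 12 h | none | none |
| 1.3.1, criterion 11 | none | 40 mg ceiling | none |
| 1.4.1.1 | about 12 h | none | none |
| 4.1.1.1 | about 12 h | none | none |
| 5.1.1.1, criterion 11 | none | 40 mg ceiling | none |
| 8.1.1.1 | none | none | none |
| 9.2 | about 12 h | none | none |

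Four of the seven give the general interval, two name methadone with a dose ceiling only, and none gives a time since the last methadone dose.

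**Step 3: do the remaining safeguards supply the missing time?**

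- COWS above 8 establishes that withdrawal has begun. It sets no clock.
- The 40 mg ceiling and prescriber clearance govern dose and suitability.
- The urine panel is collected just before induction and includes methadone, but the protocol does not say that a positive result delays dosing.
- The Substance Use Report is a day-by-day calendar, scheduled at visit 1a in Table 4.1. It records use by day and is not tied to a minimum interval in hours.
- The 4 mg initial dose, one hour of observation and same-day telephone call limit or detect harm after dosing has started.

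Each lowers the risk. None requires 24 hours since methadone.

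**Step 4: a case that passes the rule.** Take a participant whose last methadone dose, 40 mg or less for pain, was 16 hours ago and whose COWS is above 8 (the 16 hours is illustrative). The general interval is met (16 > 12), the score is met and the ceiling is met. The dose would still fall 8 hours inside the warned period (24 − 16 = 8).

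**The case against.** The best defence is that nothing here contradicts anything else. Section 12.2.1.1 discloses risks and is not a dosing instruction. The induction conditions are cumulative, and an objective withdrawal score is a reasonable way to manage the disclosed risk. The 12-hour figure is a minimum, so a clinician may wait longer. Daily substance use, opioid history and urine methadone are already collected. Whether a dose 12 to 24 hours after methadone is still hazardous once COWS exceeds 8 is a clinical question the document does not settle. The Operations Manual and the package insert in Appendix D are not shown and may set a longer interval.

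Much of this stands. The text does not instruct anyone to dose early, COWS above 8 does reduce the risk, and the unseen documents could close the gap. The induction sections, however, cite the Operations Manual only for alternative schedules of up to 16 mg on the first day. The warning in 12.2.1.1 is not qualified by COWS. The protocol also chose to pair the score with a time rule, and for methadone that time is half the interval in its own warning. Permission to wait longer does not prompt a site to do so.

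A reader might go further and infer that Phase 2 is worse, on three grounds. The document supports none of them.

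- **No interval at re-induction, so the whole 24 hours is exposed.** Sections 1.2.2.4, 8.1.1.2 and 8.1.2 call for induction, a procedure defined elsewhere in the protocol. Not repeating the conditions does not show that they lapse, and Table 4.2 schedules COWS at visit 1a.
- **An 8 mg initial dose in Phase 2 against 4 mg in Phase 1 as a defect.** Dosing for people already treated with BUP/NX is a clinical choice, and nothing in the protocol conflicts with it.
- **Entering methadone maintenance during Phase 1 leads by itself to Phase 2 dosing.** It makes the participant a Phase 1 failure, but the footnote to Table 4.1 also requires eligibility for Phase 2, and Table 4.2 schedules an eligibility review at visit 1a.

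All that can fairly be asked for Phase 2 is an explicit statement that the same pre-induction conditions apply.

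**Conclusion.** The inconsistency is real and minor. The stated rule permits induction during a period of about 12 hours that the protocol's own toxicity section warns about, and no place in the protocol shown sets a time since the last methadone dose.

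This conclusion rests on the four statements of the interval, the two statements of criterion 11 and the single statement of the warning. It assumes that neither the Operations Manual nor the package insert already imposes a longer methadone interval, which cannot be checked here. The protocol does not say how many participants will have used methadone recently or how many of them would reach a COWS above 8 within 24 hours. The number is probably small, and none is assumed.

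There is no effect on the EMM versus SMM comparison, the power or the sample size. The point is about participant safety and consistent instructions to sites.

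**What to change.** In inclusion criterion 11 (1.3.1 and 5.1.1.1) and in the induction text (1.2.1.4, 1.4.1.1, 4.1.1.1, 8.1.1.1 and 9.2), add that at least 24 hours must have passed since the last methadone dose from any source, in addition to COWS above 8. Check this at visit 1a, using the substance-use calendar and the urine methadone result already collected. Where either shows methadone, ask for the time of the last dose, because the calendar works in days. State once that the same pre-induction conditions apply to any Phase 2 induction or re-induction, including a restart under 7.4.2.2. If the Operations Manual already sets a longer methadone interval, repeat that interval in these places.

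The cost is one sentence at each named place and one question before dosing; no new test is needed. The real downside is clinical. A few participants, some already in withdrawal, would start BUP/NX up to about 12 hours later than the present text allows.
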